3.4.3. Nonstudy Vaccines and Concomitant Medications

The name and date of administration for any nonstudy vaccinations received from the time of signing of the ICD to the final visit will be collected and recorded in the CRF. Details of any medications that the participant is currently taking for medical conditions at enrollment will be recorded in the CRF. Medications taken to treat SAEs from the time of signing of the ICD to the final visit will also be collected. Nonstudy vaccines and concomitant medications will be coded using the WHODD.

3.5. Safety Endpoints

Not applicable.

4. ANALYSIS SETS (POPULATIONS FOR ANALYSIS)

Analysis populations are defined for the statistical analysis of safety and immunogenicity results in the table below. For the specified criteria in each population definition that are not associated with unblinded information (randomized or actual received vaccination), data for all participants will be assessed to determine if participants meet the criteria for inclusion in each analysis population prior to unblinding and releasing the database for the specified analysis, and the classifications will be documented per standard operating procedures.

Population	Description
Enrolled	All participants who sign the ICD.
Randomized	All participants who are assigned a randomization number in the IWR system.
Evaluable 13-matched immunogenicity	
This population was the primary analysis population for immunogenicity results of the 13 matched serotypes.
 
This population generally includes any randomized participant who:
 
 • is eligible based on inclusion and exclusion criteria • receives the first vaccine (20vPnC or 13vPnC) as randomized • has the Visit 2 blood collection within 27 to 49 days after Vaccination 1 • has at least 1 valid OPA titer for any of the 13 matched serotypes at Visit 2 • has no other major protocol deviations as determined by the clinician.

Population	Description
Evaluable 7-additional immunogenicity	
This population is the primary analysis population for immunogenicity results of the 7 additional serotypes.
 
This population generally includes any randomized participant who:
 
 • is eligible based on inclusion and exclusion criteria • receives the assigned investigational products at Visit 1 (20vPnC) for the 20vPnC/saline group or receives the assigned investigational products at both Visit 1 and Visit 2 (13vPnC and PPSV23) for the 13vPnC/PPSV23 group • has either the Visit 2 blood collection within 27 to 49 days after Vaccination 1 (20vPnC) for the 20vPnC/saline group or the Visit 3 blood collection within 27 to 49 days after Vaccination 2 (PPSV23) for the 13vPnC/PPSV23 group • has at least 1 valid OPA titer for any of the 7 additional serotypes at either Visit 2 for the 20vPnC/saline group or Visit 3 for the 13vPnC/PPSV23 group • has no other major protocol deviations as determined by the clinician.
CCI	
Safety	All participants who receive at least 1 dose of the investigational product.

The statistical analysis of immunogenicity results will be primarily based on the evaluable immunogenicity population.

CCI

Participants will be summarized according to the vaccine group to which they are randomized.

All safety analyses will be based on the safety population. Participants will be summarized by vaccine group according to the investigational products they actually receive.

Analyses of reactogenicity endpoints are based on a subset of the safety population that includes participants with any e-diary data reported after the specified vaccination.

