## **8.1. Efficacy and/or Immunogenicity Assessments**

### **8.1.1. Immunogenicity Assessments**

Blood samples (approximately 30 mL per sample) will be collected from all participants at Visit 1 (prior to administration of 20vPnC or 13vPnC), at Visit 2 (prior to administration of saline or PPSV23), and at Visit 3. Sample collection, processing, storage, and shipping information can be found in the SRM or equivalent manual.

[figure not shown]

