#### 9.1.2. Statistical Hypotheses

##### 9.1.2.1. Noninferiority Comparing Pneumococcal Serotype-Specific OPA Titers 1 Month After Vaccination (Primary Endpoint)

NI of the immune response after vaccination for each serotype in 20vPnC is evaluated by serotype-specific OPA GMTs from the 20vPnC/saline group and the 13vPnC/PPSV23 group as described below.

Hypothesis testing will be used to assess NI of the serotype-specific OPA titers after administration of 20vPnC to those after administration of the control vaccine for each 20vPnC serotype. The null hypothesis for a serotype is

$$H_0: \ln(\mu_A) - \ln(\mu_B) \leq \ln(0.5)$$

where  $\ln(0.5)$  corresponds to a 2-fold margin for NI and

- $\ln(\mu_A)$  is the natural log of the geometric mean OPA titer 1 month after 20vPnC in the 20vPnC/saline group;
- $\ln(\mu_B)$  is the natural log of the geometric mean OPA titer 1 month after 13vPnC in the 13vPnC/PPSV23 group when the serotypes is one of the 13 shared serotypes (1, 3, 4, 5, 6A, 6B, 7F, 9V, 14, 18C, 19A, 19F, and 23F) or
- $\ln(\mu_B)$  is the natural log of the geometric mean OPA titer 1 month after PPSV23 in the 13vPnC/PPSV23 group when the serotype is one of the 7 additional serotypes (8, 10A, 11A, 12F, 15B, 22F, and 33F).

The null hypothesis will be rejected and NI of 20vPnC to the control vaccine for a serotype will be declared if the lower bound of the 2-sided 95% CI for the ratio of the GMT from the 20vPnC/saline group to that from the 13vPnC/PPSV23 group for that serotype is greater than 0.5 (2-fold criterion), with control being 13vPnC for the 13vPnC serotypes and PPSV23 for the 7 additional serotypes.

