## 9.2. Sample Size Determination

Overall sample size of the study and the size from each country are based on considerations of the statistical probability of demonstrating NI of the overall immune response to 20vPnC comparing to control, a sufficient number of participants from each country for safety and immunogenicity evaluations to meet regulatory requirements of each country, and operational feasibility of the study.

Sample size and probability for the primary immunogenicity objectives are based on simulations of multivariate log-normal distributed random numbers with assumptions supported by Cohort 1 OPA results from the US pivotal Phase 3 study of 20vPnC (B7471007), as described in [Table 4](#).

Assuming the true GMRs and variance-covariance matrices for the 20 serotype-specific OPA titers are the same as that obtained from B7471007, the estimated probabilities to demonstrate NI for at least 18 out of 20, at least 19 out of 20, and for all 20 serotypes are approximately 99.3%, 94.7%, and 18.6%, respectively, assuming 630 evaluable participants in each group ([Table 5](#)). The large decrease in the probability of demonstrating NI for all 20 serotypes, compared to the probability of demonstrating at least 19 serotypes, is due to a relatively low observed GMR of 0.55 for serotype 8 in Study B7471007.

To ensure 630 evaluable participants per group for primary analysis, 700 participants per group (total 1400 participants) will be enrolled, assuming a dropout rate of about 10%.

A total of approximately 700 Japanese participants will be enrolled, and 500 and 200 participants will be enrolled from Korea and Taiwan, respectively.

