### 9.3. Analysis Sets

For purposes of analysis, the following analysis sets are defined:

Population	Description
Enrolled	All participants who have a signed ICD.
Randomized	All participants who are assigned a randomization number in the IWR system.
Evaluable 13-matched immunogenicity	All eligible randomized participants who receive the first vaccine as randomized, have Visit 2 blood collection within an appropriate window for Visit 2, have at least 1 valid OPA titer for any of the 13 matched serotypes at Visit 2, and have no other major protocol deviations as determined by the clinician.
Evaluable 7-additional immunogenicity	All eligible randomized participants who receive the assigned study interventions at Visit 1 for the 20vPnC/saline group or receive the assigned study interventions at both Visit 1 and Visit 2 for the 13vPnC/PPSV23 group, have either Visit 2 blood collection for the 20vPnC/saline group or Visit 3 blood collection for the 13vPnC/PPSV23 group within appropriate windows for Visit 2 or 3, respectively, have at least 1 valid OPA titer for any of the

Population	Description
	7 additional serotypes at either Visit 2 for the 20vPnC/saline group or Visit 3 for the 13vPnC/PPSV23 group, and have no other major protocol deviations as determined by the clinician.
CCI [REDACTED]	[REDACTED]
Safety	All participants who receive at least 1 dose of the study intervention with safety follow-up after any vaccination.

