5.2.2.2. Geometric Mean Ratios

The OPA serotype-specific antibody titer ratios (GMRs) will be calculated for each of the noninferiority assessments as:

The GMT ratio of 20vPnC/saline to 13vPnC/PPSV23:

- ratio of the GMT from the 20vPnC/saline group to that from the 13vPnC/PPSV23 group at Visit 2 for the 13 matched serotypes.

- ratio of the GMT from the 20vPnC/saline group at Visit 2 to that from the 13vPnC/PPSV23 group at Visit 3 for the 7 additional serotypes.

Details regarding the derivation of GMRs are provided below in Table 6.

Table 6. Derivation of Serotype-Specific OPA GMRs at 1 Month After Vaccination

Comparison	Analysis Population	Serotypes	Numerator	Denominator
Between-vaccine group comparison	Evaluable 13-matched immunogenicity population	13 matching serotypes	20vPnC/saline group at Visit 2	13vPnC/PPSV23 group at Visit 2
	Evaluable 7-additional immunogenicity population	7 additional serotypes	20vPnC/saline group at Visit 2	13vPnC/PPSV23 group at Visit 3

Abbreviations: GMR = geometric mean ratio; OPA = opsonophagocytic activity.

For each comparison above, there will be 2 approaches to calculating the GMR and CI for each serotype:

Model-Based GMR

The primary approach will be based on a linear regression model. Specifically,

- For the comparison of OPA results, the following terms will be included in the regression model: corresponding baseline OPA titer, age, sex (male or female), country (Japan, Korea, or Taiwan), smoking status (current smoker, ex-smoker, or never smoked), and vaccine group.

The difference between these LS means of OPA titers on the natural log scale and associated CI estimated from the linear regression model will be exponentiated to obtain the GMR and CI.

CCI

[figure not shown]
A 2-sided 95% CI will be used for the noninferiority comparison of the 20vPnC/saline group to the 13vPnC/PPSV23 group.

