6.5.2. Study Conduct and Participant Disposition

6.5.2.1. Participant Disposition

The number and percentage of randomized participants will be included in the participant disposition summary. In addition, the numbers and percentages of participants who received vaccination(s) at Visit 1 and at Visit 2; who completed participation through Visit 3; who completed the study; and who withdrew from the study, along with the reasons for withdrawal, will be tabulated by vaccine group (according to randomized group assignment). The reasons for withdrawal will be those as specified in the database.

Participants excluded from each analysis population will also be summarized separately, along with the reasons for exclusion, by vaccine group.

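### Does the evaluable 7-additional set tilt the serotype 8 noninferiority test by requiring a second injection and a Visit 3 sample of controls only?

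*SAP*

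**What the plan says.** SAP 4 defines the evaluable 7-additional population by group. On dosing, a participant "receives the assigned investigational products at Visit 1 (20vPnC) for the 20vPnC/saline group or receives the assigned investigational products at both Visit 1"; the sentence ends with the second visit, at which controls receive PPSV23. On sampling, the 20vPnC/saline group needs a Visit 2 sample 27 to 49 days after Vaccination 1, and controls need "the Visit 3 blood collection within 27 to 49 days after Vaccination 2 (PPSV23) for the 13vPnC/PPSV23 group". Protocol 9.3 has the same structure: participants must "have either Visit 2 blood collection for the 20vPnC/saline group or Visit 3 blood collection for the 13vPnC/PPSV23 group within appropriate windows".

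This population carries the formal tests for the seven additional serotypes. Noninferiority is shown "if the lower bound of the 2-sided 95% CI for the ratio of the GMT from the 20vPnC/saline group" over the control GMT exceeds 0.5 (Protocol 9.1.2.1). The primary regression contains "corresponding baseline OPA titer, age, sex (male or female), country (Japan, Korea, or Taiwan), smoking status" and vaccine group (SAP 5.2.2.2). Missing serology is not imputed.

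Blood is drawn from all participants at Visit 1, "at Visit 2 (prior to administration of saline or PPSV23), and at Visit 3" (Protocol 8.1.1). On reporting, SAP 6.5.2.1 states: "Participants excluded from each analysis population will also be summarized separately, along with the reasons for exclusion, by vaccine group". SAP 6.5.2.2 adds the numbers sampled inside and outside the time frames, by group.

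**The concern.** Read quickly, the rule looks lopsided. A control must come through Vaccination 2 and about another month of follow-up; a 20vPnC participant is finished, for this analysis, at the Visit 2 draw. Loss after that draw removes controls only. All adjustment covariates are measured at baseline, so the model cannot correct for selection that depends on what happens after Vaccination 1.

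At stake would be serotype 8. Protocol 9.2 attributes the low chance of success on all 20 serotypes to the "relatively low observed GMR of 0.55 for serotype 8 in Study B7471007". If the lost controls were stronger responders, the retained control GMT would be too low and the GMR too favourable to 20vPnC. If they were weaker, the error would run the other way. No readable passage re-estimates the serotype 8 GMR under a different inclusion rule.

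**Working it through.** **1. Who is in and who is out.** Applying SAP 4 to the situations that can arise, with the eligibility and major-deviation criteria taken as met in both arms:

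| Situation | 20vPnC/saline | 13vPnC/PPSV23 |
|---|---|---|
| Visit 2 missed altogether | out (no Visit 2 titre) | out (no PPSV23) |
| Visit 2 late (say day 55), injection given, Visit 3 sample on time | out | in |
| Visit 2 injection given but no Visit 2 draw, Visit 3 sample on time | out | in |
| Visit 2 sample in window, second injection withheld | in | out |
| Visit 2 complete, Visit 3 sample missed or out of window | in | out |

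The exclusions run in both directions, and missing Visit 2 removes participants from either arm. In each arm the rule asks for the product under comparison, a sample 27 to 49 days after it and a valid titre. The difference in visits comes from the comparison itself: Visit 2 titres after 20vPnC against Visit 3 titres after PPSV23.

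**2. The plan's own figure.** From Protocol Table 4, serotype 8: GMTs 540.2 (95% CI 493.9 to 591.0, n = 1374) and 978.1 (896.8 to 1066.8, n = 1319).

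- SD of ln titre = sqrt(n) × ln(upper/lower) / (2 × t), giving 1.696 and 1.607.
- SE at 630 per group = sqrt((1.696² + 1.607²)/630) = 0.0931.
- GMR = 540.2/978.1 = 0.552; ln(0.552/0.5)/0.0931 is about 1.07.
- Power = Phi(1.07 − 1.96) = 18.6%. The protocol states 18.6% for 20 of 20, which serotype 8 limits.
- Expected lower bound = 0.552 × exp(−1.962 × 0.0931) = 0.460.
- Observed GMR needed to pass = 0.5 × exp(1.962 × 0.0931) = 0.600.

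**3. How far a net control loss could move the result.** Let f be the excess control fraction lost and r the fold difference in titre between lost and retained controls. The ln GMR then shifts by f × ln(r). Neither quantity is documented; I assume f = 0.01 to 0.04 and r = 1.5 to 2.

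- Smallest shift: 0.01 × ln 1.5 = 0.0041. Largest: 0.04 × ln 2 = 0.0277. The GMR moves by 0.4 to 2.8%.
- Chance of passing at the planning values: 17.5% or 19.8% for the smallest shift, 11.7% or 27.6% for the largest, according to direction.
- Verdict-changing band at the largest shift: 0.600 × exp(±0.0277) = 0.584 to 0.617.
- Titre ratio needed to lift the expected lower bound from 0.460 to 0.5 at 4% loss: exp(ln(0.5/0.460)/0.04), about 8-fold.
- Lost precision is negligible: 605 controls instead of 630 gives 18.3% power.
- The other six serotypes have planning GMRs of 1.41 to 3.03 and power of about 100%.

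**4. Whether Table 4 shows such a loss.** The mean ratio of control to 20vPnC counts is 0.979 for the seven serotypes (range 0.944 to 1.038) and 0.990 for the thirteen. Controls outnumber 20vPnC for 11A (1209 against 1198) and 33F (1201 against 1157). These counts depend on valid assay results as well as attendance, so they do not measure Visit 3 loss.

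**5. Whether the obvious remedy would detect it.** Suppose 20vPnC participants also had to receive saline and give an in-window Visit 3 sample. They would then need two in-window samples and controls one, so the sets would still differ. No lost control returns; valid Visit 2 titres are discarded for later events.

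Removing k of 630 at random moves the mean ln titre with SD 1.696 × sqrt(1/(630 − k) − 1/630):

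- k = 6 (about 1%): 0.0066, against an assumed bias of 0.0041 to 0.0069.
- k = 25 (about 4%): 0.0137, against 0.0162 to 0.0277.

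The bias sought is 0.6 to 2.0 times the noise from the trimming itself. A lower bound that crossed 0.5 could do so by chance.

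**The case for a change.** The strongest case is that the documents describe a non-random route out. Participants with significant reactions after Visit 1, or with adverse events judged to raise risk, receive no further vaccination (Protocol 2.3.1), and those who cease to be eligible stop vaccination (Protocol 7.1). Such a control leaves this set; a similar 20vPnC participant with an in-window Visit 2 sample is not removed by the dosing and sampling conditions. Baseline covariates need not absorb the difference. At a true serotype 8 GMR of exactly 0.5, 4% loss of controls with twofold higher titres would raise the one-sided error from 2.5% to 4.8%. At 10% loss the figure is 10.8%, and the pass probability at the planning GMR ranges from 5.0% to 42.3%.

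The mechanism stands, as does the point that the interval after Visit 2 exposes controls alone. The figures are conditional on assumptions. The 10% case sets the excess in one arm equal to the whole nonevaluable allowance in Protocol 9.2 (630/0.90 = 700 per group). Nothing indicates that lost controls respond more strongly rather than more weakly, and in the latter case the shift works against 20vPnC.

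Nor can absence of a supportive analysis be shown. A redacted row follows the 7-additional set in SAP 4 and Protocol 9.3. SAP 5.2.2.2 announces two ways of calculating the GMR, of which one is readable. The analysis-set line in SAP 6.1.2.1 runs into a redaction. A broader population there could bring back controls excluded for window or deviation reasons, though not those with no Visit 3 titre.

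**Conclusion.** The concern does not hold. The arm-specific conditions follow from comparing a Visit 2 titre with a Visit 3 titre, and they exclude participants from both arms for different reasons. The net effect is undocumented in size and direction. Under the assumed 1 to 4% excess loss and 1.5- to 2-fold titre difference it moves the GMR by at most 2.8%, which matters for serotype 8 alone and only for an observed GMR of about 0.584 to 0.617. These figures use unadjusted SDs from the earlier trial; the baseline-adjusted model may give a smaller SE.

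The protocol's power figures reproduce, and the prespecified set and decision rule are clear. The tabulations in SAP 6.5.2.1 and 6.5.2.2 will show any imbalance by arm. What remains is a preference for one further supportive run, which would not recover the missing controls and would leave the primary decision unchanged.

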- b. Blood sample will be collected prior to vaccination at Visits 1 and 2.
- c. Participants will record in an e-diary prompted local reactions and systemic events occurring within 10 and 7 days, respectively, after Vaccination 1. Use of antipyretic/pain medications will also be prompted for and collected daily in an e-diary for 7 days after Vaccination 1. In addition, participants enrolled at Japan sites will record prompted local reactions and systemic events and use of antipyretic/pain medications in an e-diary after Vaccination 2 (collection periods will be the same as the collection periods after Vaccination 1). Participants will be instructed to contact the study staff or investigator if they experience redness or swelling measuring >20 measuring device units or severe pain at the injection site or any Grade 4 prompted systemic event.
- d. Designated site staff will review e-diary data online at frequent intervals (daily is optimal) for the 10 days following Vaccination 1 and Vaccination 2 (Japan sites only) to evaluate participant compliance and reported events as part of the ongoing safety review. Any e-diary devices given to participants are to be collected no later than Visit 2 and Visit 3 (Japan sites only).
- e. Only Japan sites.
- f. Korea and Taiwan sites.
- g. If the participant consents, participants withdrawn from the study will receive a 1-month safety follow-up after their last dose of study intervention for collection of any SAEs.

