## 3. OBJECTIVES, ESTIMANDS, AND ENDPOINTS

Objectives	Estimands	Endpoints
Primary Safety	Primary Safety	Primary Safety
To describe the safety profile of 20vPnC.	
In participants receiving at least 1 dose of study intervention and having safety follow-up after vaccination from each vaccine group:
 
 
• The percentage of participants reporting prompted local reactions within 10 days after the first vaccination (20vPnC or 13vPnC)
 
• The percentage of participants reporting prompted systemic events within 7 days after the first vaccination (20vPnC or 13vPnC)
 
• The percentage of participants reporting AEs within 1 month after vaccination with 20vPnC or 13vPnC
 
• The percentage of participants reporting SAEs within 1 month after vaccination with 20vPnC or 13vPnC
 
	
 
• Prompted local reactions (redness, swelling, and pain at the injection site)
 
• Prompted systemic events (fever, headache, fatigue, muscle pain, and joint pain)
 
• AEs
 
• SAEs
 

Primary Immunogenicity	Primary Immunogenicity	Primary Immunogenicity
To demonstrate that the immune responses to the 13 serotypes in 13vPnC (1, 3, 4, 5, 6A, 6B, 7F, 9V, 14, 18C, 19A, 19F, and 23F) induced by 20vPnC are noninferior to the immune response induced by 13vPnC.	In participants in compliance with the key protocol criteria (evaluable participants): 
 
For each of the 13 serotypes: GMR of serotype-specific OPA titers 1 month after 20vPnC to the serotype-specific OPA titers 1 month after 13vPnC
 
	
 
Serotype-specific OPA titers
 

To demonstrate that the immune responses to the 7 additional serotypes in 20vPnC (8, 10A, 11A, 12F, 15B, 22F, and 33F) induced by 20vPnC are noninferior to the immune response induced by PPSV23.	In evaluable participants: 
 
For each of the 7 additional serotypes: GMR of serotype-specific OPA titers 1 month after 20vPnC to the serotype-specific OPA titers 1 month after PPSV23
 
	
 
Serotype-specific OPA titers
 

Secondary Immunogenicity	Secondary Immunogenicity	Secondary Immunogenicity

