## 8.2. Safety Assessments

A clinical assessment, including medical history and measurement of oral temperature, will be performed on all participants prior to vaccination to determine participant eligibility and to establish a clinical baseline. Significant medical history, significant findings from any physical examination, if performed, and temperature measurements will be documented and recorded in the source documents and/or the CRF.

The participant will be observed for 30 minutes after each study vaccination and any reactions occurring during that time will be recorded as AEs.

Prompted e-diary events, including local reactions (redness, swelling, and pain at the injection site) and systemic events (fever, headache, fatigue, muscle pain, and joint pain) that occur 10 and 7 days, respectively, after study intervention administration (where Day 1 is the day of vaccination) are graded as described in [Section 8.2.2.1](#) and [Section 8.2.2.2](#). Furthermore, AEs and SAEs will be collected as defined in [Section 8.3](#).

Planned time points for all safety assessments are provided in the SoA. Unscheduled clinical laboratory measurements may be obtained at any time during the study to assess any perceived safety issues.

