2.1. Study Objectives, Endpoints, and Estimands

The estimands corresponding to each primary and secondary objective are described in [Table 2](#). The estimands to evaluate the immunogenicity objectives for NI are based on evaluable populations (see [Section 4](#) for definition). These estimands estimate the vaccine effect in the hypothetical setting where participants follow the study schedules and protocol requirements as directed. The estimand addresses the objective of estimating the maximum potential difference between 2 groups, 20vPnC/saline and 13vPnC/PPSV23, since the impact of noncompliance is likely to diminish the observed difference between the 2 groups. Missing serology results will not be imputed. Immunogenicity results that are below the LLOQ will be set to $0.5 \times \text{LLOQ}$ in the analysis.

In the primary safety objective evaluations, missing AE start dates will be imputed according to Pfizer safety rules (Section 5.3). No other missing information will be imputed in the safety analysis.

Table 2. List of Primary, Secondary, CCI Objectives, Endpoints, and Estimands

Primary Safety Objective	Primary Safety Estimands	Primary Safety Endpoints
To describe the safety profile of 20vPnC.	In participants receiving at least 1 dose of investigational product and having safety follow-up after vaccination from each vaccine group: 
 • The percentage of participants reporting prompted local reactions within 10 days after the first vaccination (20vPnC or 13vPnC) • The percentage of participants reporting prompted systemic events within 7 days after the first vaccination (20vPnC or 13vPnC) • The percentage of participants reporting AEs within 1 month after vaccination with 20vPnC or 13vPnC • The percentage of participants reporting SAEs within 1 month after vaccination with 20vPnC or 13vPnC 	
 • Prompted local reactions (redness, swelling, and pain at the injection site) • Prompted systemic events (fever, headache, fatigue, muscle pain, and joint pain) • AEs • SAEs
Primary Immunogenicity Objectives	Primary Immunogenicity Estimands	Primary Immunogenicity Endpoints

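### Does the missing follow-up condition in the SAP Section 4 safety population leave the adverse event denominators unsettled?

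*SAP*

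**What the plan says.** The analysis set in SAP Section 4 has one condition: "All participants who receive at least 1 dose of the investigational product". The same section adds that "All safety analyses will be based on the safety population".

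Three other places add a second condition:

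- SAP Section 2.1, Table 2, for the primary and secondary safety estimands: "In participants receiving at least 1 dose of investigational product and having safety follow-up after vaccination from each vaccine group".
- Protocol Section 3, for the same estimands: "In participants receiving at least 1 dose of study intervention and having safety follow-up after vaccination from each vaccine group".
- Protocol Section 9.3, in the safety set itself: "All participants who receive at least 1 dose of the study intervention with safety follow-up after any vaccination".

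Neither document states the minimum contact or data that makes a participant count as followed up. Protocol Section 8.2 describes contact that every dosed participant should have: "The participant will be observed for 30 minutes after each study vaccination and any reactions occurring during that time will be recorded as AEs". The Schedule of Activities, note g, uses the term for something later and longer: if they consent, "participants withdrawn from the study will receive a 1-month safety follow-up after their last dose of study intervention for collection of any SAEs".

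For prompted local and systemic events, SAP Section 4 has a separate rule: "Analyses of reactogenicity endpoints are based on a subset of the safety population that includes participants with any e-diary data reported after the specified vaccination".

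**The concern.** The SAP appears to give one population for the safety estimands and a different one for their analysis. The permission in SAP Section 2 to modify the protocol explains a difference between the two documents. It does not explain a difference between two sections of the SAP.

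AEs and SAEs within a month of the first vaccination are primary safety endpoints, and their tables report both numerator and denominator. If one programmer followed Section 4 and another followed Table 2 or Protocol Section 9.3, they could arrive at different denominators and different exclusion tables. With safety follow-up undefined, the second programmer would also have to decide whether a participant seen only during the 30-minute observation belongs in the set. At stake would be the denominator of the headline AE and SAE percentages.

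**Working it through.** **Which text governs the tables**

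| Place | Dose required | Follow-up required | Role |
|---|---|---|---|
| SAP Table 2 | yes | yes | summary of objectives and estimands |
| Protocol Section 3 | yes | yes | summary of objectives and estimands |
| Protocol Section 9.3 | yes | yes | set definition, which the SAP may modify |
| SAP Section 4 | yes | no | set definition for the analysis |
| SAP 6.1.1.3 (AEs) | by reference to Section 4 | no | directs the AE tables |
| SAP 6.1.1.4 (SAEs) | by reference to Section 4 | no | directs the SAE tables |

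Both analysis sections point to Section 4 by number, and both restate the estimand without the follow-up condition. An analyst working through SAP Section 6 reaches one answer, all dosed participants, and never has to define safety follow-up.

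**Who could be counted differently**

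Only a participant who was dosed and then had no qualifying follow-up. If the 30-minute observation qualifies, this group is empty or nearly so. If later contact is needed, it is those dosed and never reached again. Their number is not in the documents, so it is an assumption below.

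**Size**

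The plan's own figure comes first. Protocol Section 9.2 wants 630 evaluable per group with about 10% dropout: 630 / (1 − 0.10) = 700 per group, 1400 in total, as stated.

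Let N = 700 be dosed per group, m be those without follow-up (and with no recorded event), and x be the participants with an AE. The two percentages are x / N for all dosed and x / (N − m) with follow-up required. The gap is x/(N − m) − x/N = (x/N) × m/(N − m). The intervals are Clopper-Pearson, as the SAP specifies.

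| m (share of group) | x = 70 | x = 210 |
|---|---|---|
| 0 | 70/700 = 10.00% (7.88 to 12.47) | 210/700 = 30.00% (26.62 to 33.55) |
| 1 (0.14%) | 70/699 = 10.01% (7.89 to 12.48) | 210/699 = 30.04% (26.66 to 33.59) |
| 7 (1%) | 70/693 = 10.10% (7.96 to 12.59) | 210/693 = 30.30% (26.90 to 33.88) |
| 14 (2%) | 70/686 = 10.20% (8.04 to 12.72) | 210/686 = 30.61% (27.18 to 34.21) |
| 35 (5%) | 70/665 = 10.53% (8.30 to 13.11) | 210/665 = 31.58% (28.06 to 35.26) |

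The last row is deliberately severe: 35 is half of the 70 per group (700 − 630) allowed for every cause of being non-evaluable. Even there, the shift of 0.53 or 1.58 points is well inside the half-width of the interval, which is about 2.3 points at 10% [(12.47 − 7.88)/2] and 3.5 points at 30% [(33.55 − 26.62)/2].

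**Tier 2 classification**

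A preferred term is Tier 2 if at least 1% of a group reports it, so the minimum count is 0.01 × N rounded up. At 700 it is 7, and at 693 it is also 7 (6.93 rounded up). This does not hold for every N. With 704 dosed and 7 lacking follow-up, the minimum is 8 (7.04 rounded up) against 7 (6.97 rounded up). A term reported by exactly 7 could then change tier. The consequence is whether a confidence interval for the group difference accompanies that term.

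**The case for a change.** The strongest case for acting is that the inconsistency lies within the SAP, that the text on both sides is complete and visible, and that three of the four population statements carry the follow-up condition. The visible part of the SAP change log mentions no change to the safety set, so one cannot show that the shorter definition was deliberate. The 30-minute observation does not settle it either, because elsewhere the term points to later collection. Aligning the wording would take one clause and would spare a query about a primary safety denominator.

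The textual part of this stands: the wording is not aligned, and the term has no membership definition. The consequence does not follow. The change log is partly redacted, so its silence shows nothing in either direction. The note in the Schedule of Activities concerns SAE collection in withdrawn participants who consent; it is a procedure and does not decide who belongs in an analysis set. The undefined term matters only for someone applying the longer definition, and the SAP's AE and SAE sections do not call for that. Nor is there room to pick the set after seeing results: SAP Section 4 has membership criteria that do not depend on unblinded information assessed and documented before unblinding, and SAP 6.5.2.1 tabulates exclusions from each population with reasons, by vaccine group.

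One further point is fair. Counting all dosed participants treats anyone lost straight after vaccination as free of events, which pulls the percentage down slightly. The table above gives the size of that effect.

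**Conclusion.** The concern is right about the words and does not call for a change to the plan. The follow-up condition in SAP Table 2 reads as wording carried over from the protocol, while the SAP text that controls the AE and SAE tables consistently points to an all-dosed population. Following the SAP as written gives a complete and conventional descriptive safety analysis, with n and N shown. Either definition would be acceptable, so choosing between them brings no gain.

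For 1% of a group without follow-up, an AE percentage between 10% and 30% moves by 0.10 to 0.30 point. For 5% it moves by 0.53 to 1.58 points. If the 30-minute observation counts, the movement is about zero. These figures assume 700 dosed per group and no recorded events among those without follow-up; their number and the event rates are illustrative. The safety objective has no formal test, the noninferiority analyses use other populations, and the reactogenicity tables have their own data rule. No conclusion of the trial turns on this.
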